#### Secondary efficacy outcomes in detail

1. Percent hair regrowth from baseline determined by SALT measurements following 12, 24 weeks of treatment and during the observational phase at weeks 36 and 48.
2. Comparison of the proportion of responders in the experimental group with the historically known placebo response rate ( $<10\%$ ), with response defined as 50% change in SALT score (50% regrowth) from baseline, at weeks 12, 36 and 48.
3. Comparison of the proportion of subjects in the experimental group and the proportion of subjects in the historical control group attaining global overall improvement SALT score of A5 (100% coverage) supported by  $\leq$  SALT 25 at weeks 12, 24, 36 and 48.
4. Change in PGA (Physician Global Assessment) based on evaluation of live evaluations and standardized photographs between baseline, week 12, 24, 36 and 48.
5. Change in patient global assessment between baseline, Week 12, 24, 36 and 48.
6. Change in patient quality of life assessment from baseline to weeks 12, 24, 36 and 48.
7. Frequency of occurrence and timing of relapse (as defined above) in responders followed for 6 months off therapy.
8. Safety will be evaluated as a secondary endpoint using descriptive statistics to summarize the cumulative incidence and types of AEs.
9. The proportion of patients who discontinued treatment will be summarized.

[figure not shown]
### **6.4.3 Other Assessments**

#### Photography

Photography will be performed using a high-resolution digital camera with Intelliflash system from Canfield Scientific, Inc., mounted on a stereotactic arm. Patients will be positioned using a fixed guide, after which photographs of the entire scalp will be taken at standardized locations and at a fixed distance. Close-up photographs may also be taken using an epiluminescent attachment in order to assess for the presence of early regrowth.

#### Biopsy

All punch biopsies will be performed by the study doctor at a specific location and time point according to the schedule of study assessments. The biopsy site will be anesthetized with an injection of 1% lidocaine with epinephrine. After approximately 1 minute, the physician applies pressure to the biopsy site using a 4 mm skin punch (a sterile cylindrical tube with a sharp edge). The punch is twisted until the blade of the skin punch has pierced the epidermis and dermis of the skin and enters the subcutaneous fat. Depending on the thickness of the skin in the area being biopsied, the cylindrical blade may be buried to the hub (approximately 6mm). After the blade has sufficiently cored or carved out a cylinder of skin, the skin punch is removed. Nontraumatic forceps are used to gently grasp the cored skin, pulling upward to remove the core and reveal the subcutaneous fat. Scissors are used to cut the cored tissue free from the underlying subcutaneous fat. The specimen is placed immediately into the appropriate media. Once the specimen has been removed, pressure is applied to the biopsy site with a sterile 2 x 2 gauze. The biopsy site is then closed with several simple interrupted sutures. Either an absorbable or nonabsorbable suture may be used at the investigators discretion. Antibiotic ointment is applied and the area is covered with a standard BandAid or sterile gauze and paper tape. When necessary, a small pressure dressing may be applied. Subjects will be instructed in wound care and will be advised to call the research unit if they have any concerning signs or symptoms during healing.

### Biosamples

A recent histological/gene expression study of synovial biopsies from RA patients treated with abatacept noted only mild changes in cellular synovial infiltrates during treatment. However, marked changes in IFN- $\gamma$  expression was identified, with significant reductions only seen in the clinically responding patients (Buch et al. 2009). The decrease in IFN- $\gamma$  production in the responders implies that functional inhibition of T cell activity is important for therapeutic outcome. Our proposed studies will include longitudinal biopsies that could provide additional support for interferon- $\gamma$  modulation and abatacept treatment outcome.

Our procurement of serial biopsies, sera and PBMCs obtained at baseline and during treatment will provide the opportunity to correlate resolution of inflammatory biomarkers with treatment response in AA.

Biosamples will be obtained upon entry and again after 4 weeks, 12 weeks and 24 weeks of treatment and optional blood collection timepoints. Biospecimens at each time point will include: 1) a 4 mm skin biopsy; 2) 5 ml of blood for serum; 3) 60 ml of blood for PBMCs.

Blood volumes for research: 60 ml of blood is required to insure that sufficient viable cells are available after thawing of cryopreserved PBMC aliquots to enable functional T cell studies in triplicate. Our experience is that viable recovery of PBMC in freeze-thawed specimens is highly variable and range from 0.1-1.0 x 10^6 per ml of blood. Our blood volume obtained for research is 65 ml at one time, a maximum of 130 ml in a 4 week period and 260 ml in total over 6 months.

### Biomarker Assessment and Clinical Correlative Studies

Our mechanistic studies are focused on correlating treatment and disease status with;

- 1) histological improvement of T cell infiltrates;
- 2) reduced IFN responses in the skin and blood;
- 3) reduced HF NKG2DL expression; and
- 4) declines in circulating and peribulbar CD4+ and CD8+NKG2D+ infiltration.
- 5) AA GWAS risk haplotype susceptibility

Previous studies in AA have reported elevated NKG2D expression in circulating CD8 T cells and NK cells (Ito et al. 2008), supporting the feasibility of our approach. Here we will be able to correlate the numbers of CD8+NKG2D+ cells in the blood with those infiltrating the target organ of patients with each other and as a function of disease status. The limited studies proposed here seeking an association of IFN- $\gamma$  cells in+NKG2D+ positive cells and clinical outcome will not, however, exhaust the “biobank” and all human materials [frozen biopsy tissue & RNA, serum and the remaining (90%) of PBMCs] will remain banked and available for future hypothesis driven questions.

Flow Cytometry Studies. The presence of CD8+NKG2D+ cells will be tracked in the blood and in the skin during treatment with Abatacept. By assessing CD8+NKG2D+ involvement in longitudinally obtained skin biopsies at baseline and during treatment we can correlate disease severity and clinical response (progression or regression) with immunopathological evidence of resolution of total cellular infiltration (by H&E) or loss of specific CD8+NKG2D+ cells in the skin (by IF) or in the blood (flow studies). CD8+NKG2D+ frequency in the peripheral circulation will be quantified using freshly isolated PBMCs obtained from 30 mls of blood obtained upon scheduled and optional blood collection timepoints. A portion of the PBMCs 2x10^6 cells will be stained with anti-CD4, anti-CD8, anti-CD25, anti-CD28 and anti-NKG2D antibodies, stimulated with PMA/ionomycin in the presence of brefeldin and stained with anti-FOXP3 and anti-IFN- $\gamma$  Abs. The remaining PBMCs will be used for RNA analysis (see below) and viably frozen for future ancillary studies. We will seek evidence of a comparable pathogenic T cell subset in the human that we observed in C3H mice, namely an activate CD25+ IFN- $\gamma$ -producing CD8+NKG2D+ T cell.

Histology and Immunofluorescence Analysis. As shown in previous studies (Ito et al. 2008; Petukhova et al. 2010) in active AA NKG2D ligands are upregulated on hair follicles in association with peribulbar NKG2D-bearing CD8+ T-cells and natural killer cells. We will seek evidence of resolution of total cellular infiltration (by H & E) and loss of specific CD8+NKG2D+ cells (by IF) and NKG2D ligands by comparing baseline biopsies with biopsies obtained on treatment after 4,

12, 24 and 36 weeks. Frozen sections will be stained with anti-CD4, anti-CD8, anti-CD56, anti-NKG2D and anti-IFN-g antibodies to visualize the total number of leukocytes, cytotoxic T-cells and NK cells present in the baseline and drug treated skin, respectively. Immunostaining with anti-ULBP3, anti-MICA antibodies and recombinant NKG2D soluble receptor (NKG2D-Ig, detects all NKG2D ligands, R & D systems) will determine whether NKG2DL “danger/stress” signals are down modulated.

Punch biopsies from patient skin before and after treatment will be embedded in OCT and 7-8 micron frozen sections will be cut. The sections will be fixed in 4% paraformaldehyde and stained overnight with primary antibodies for NKG2D ligands, receptor and immune markers. The following day, sections will be treated for 1 hr with fluorescence labeled antibody, counter-stained and mounted with DAPI containing media. Frozen sections will also be used to for H&E staining. The total number of immune cells, as well as NKG2D bearing cells, will be quantified by counting stained cells per magnification field using the NIH imaging software ImageJ and a student T-test will be carried out to determine significant changes in the number of infiltrating, NKG2D bearing immune cells to quantitatively correlate the simultaneous presence or absence of these cells in lesional skin and in circulation (by flow) during active disease or in remission.

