## **5.4 Blinding/Unblinding**

Not applicable.

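### Section 6.4.3 specifies no masking of the reader who counts infiltrating cells, so the exploratory tissue change and its correlation with regrowth could partly reflect reader expectation

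*Combined protocol and SAP*

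**What the plan says.** Under Histology and Immunofluorescence Analysis in Section 6.4.3, frozen sections from punch biopsies are stained, and total immune cells and NKG2D-bearing cells "will be quantified by counting stained cells per magnification field using the NIH imaging software ImageJ". For the analysis, "a student T-test will be carried out to determine significant changes in the number of infiltrating, NKG2D bearing immune cells". The contrast is made "by comparing baseline biopsies with biopsies obtained on treatment after 4", 12, 24 and 36 weeks. The aim is worded in one direction: "We will seek evidence of resolution of total cellular infiltration (by H & E) and loss of specific" CD8+NKG2D+ cells by immunofluorescence. The list of mechanistic aims earlier in 6.4.3 likewise speaks of histological improvement, reduced NKG2DL expression and declining infiltration.

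The link to clinical outcome is in the Flow Cytometry paragraph, where the team plans to "correlate disease severity and clinical response (progression or regression) with immunopathological evidence of resolution of total cellular infiltration". The Biosamples text adds that serial samples "will provide the opportunity to correlate resolution of inflammatory biomarkers with treatment response in AA".

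The plan does not say who counts, how many fields are read, how they are chosen, what ImageJ threshold applies, in what order sections are read, or whether they are coded. Section 5.4 Blinding/Unblinding reads "Not applicable". The one rule about raters, in Section 4.1, asks for the same investigator at each visit where possible. It covers the scalp examination, SALT and photographs, and it is about inter-rater variability, not masking.

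**The concern.** A count per field depends on which fields are taken and which stained objects are accepted as cells. ImageJ makes the tally more repeatable, but those two judgements stay with the reader. A reader who knows that a section is from week 24 can, without intending to, choose sparser fields or accept fewer cells. A reader who knows that the patient regrew hair can do so selectively in responders. The first lowers on-treatment counts in general; the second creates an association between counts and response.

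What is at stake is the mechanistic reading of a 15-patient, single-arm, open-label pilot. Tissue evidence that the infiltrate resolves, and resolves where hair returns, would support a drug effect over spontaneous regrowth or a generous clinical rating. It gives that support only if it was read independently of those expectations. The expected effect may also be modest: the Biosamples text cites synovial biopsies from abatacept-treated rheumatoid arthritis patients in which cellular infiltrates changed only mildly. A small reading bias could therefore be as large as the effect sought.

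**Working it through.** The plan gives no figure for the histology analysis, so there is none to reproduce. The check has two parts.

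**Text.** The sections on biopsy, biosamples, histology, flow cytometry, blinding, visit assessments and statistics contain no provision for coded slides, a masked or independent reader, a random reading order or a field-selection rule. The before-after test and the hoped-for direction are in the histology text. The correlation with clinical response is in the flow cytometry text, which names infiltration on H&E and CD8+NKG2D+ cells in skin and blood.

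**Illustration of size, before-after change.** Inputs:
- n = 15 pairs, from the accrual goal, assuming every patient gives both biopsies.
- True change zero; two-sided 5% paired t-test on log counts. These are assumptions, because the plan says only Student t-test.
- Within-pair SD s = 0.4, 0.6 or 0.8 log units (assumed).
- On-treatment sections under-counted by a fraction b = 0.10 or 0.20 (assumed).

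The bias on the log scale is −ln(1 − b), which is 0.105 for b = 0.10 and 0.223 for b = 0.20. The test statistic then follows a noncentral t distribution with n − 1 = 14 degrees of freedom and noncentrality −ln(1 − b)/s × √n. For b = 0.10 and s = 0.4 this is 0.105/0.4 × √15 = 1.02. The false-positive rate is the probability that |t| exceeds 2.145.

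| Pairs | Under-count | s = 0.4 | s = 0.6 | s = 0.8 |
|---|---|---|---|---|
| 15 | 10% | 15.8% | 9.7% | 7.6% |
| 15 | 20% | 52% | 27% | 17% |
| 10 | 10% | 11.6% | 7.9% | 6.6% |
| 10 | 20% | 35% | 18% | 12% |

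The 10-pair rows use the same formula with 9 degrees of freedom and critical value 2.262. A separate simulation with 15 pairs and 20,000 runs gave 17% for a 20% under-count at SD 0.8, which agrees, and about 5% with no bias.

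**Illustration of size, association with response.** Assume 6 responders and 9 non-responders, no true association, only responders' on-treatment sections under-counted, and a two-sample t-test on the log ratios. By simulation, a 20% under-count gives a false association in 25%, 12% or 8% of trials for SD 0.3, 0.5 or 0.8. A 30% under-count gives 55%, 24% or 12%. At a 20% under-count and the same SDs, the before-after test is falsely significant in 76%, 36% or 17% of trials. The correlation is thus harder to produce falsely than the change.

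**The case against.** The strongest reply is that the plan is silent, not wrong. It never says that the reader knows visit or response, and coding of slides is often left to a laboratory manual. That stands, and it limits the point to masking that is not specified.

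A reader might infer from Section 5.4 that the protocol rules out masked reading. It does not: that entry sits in the chapter on treatments and naturally means that treatment is not blinded in a single-arm trial. It says nothing about laboratory readers either way.

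A reader might also infer that the laboratory measures are the only outcomes that could be read independently of the clinical rating, or that all of them are compromised. Neither is supported. Standardized scalp photographs are taken at every scheduled visit and could equally be read under code. The qPCR and serum chemokine assays involve no choice of fields and can still corroborate a response. For flow cytometry no gating method is described, so a reader effect there is only a possibility.

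Nor does the plan make a firm prediction that these counts will fall. It seeks evidence of resolution; the sentence that states an expectation concerns gene expression. A hoped-for direction is enough for expectation bias to operate, however.

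The size of the effect is assumed throughout, and with 10 pairs and a 10% under-count the inflation is slight at the larger SDs. The outcome is also exploratory and is not among the endpoints in Section 7.3. Both points stand and lower the weight of the concern, but they do not remove it, because the remedy is so cheap.

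**Conclusion.** The point holds in a limited form. Followed as written, Section 6.4.3 leaves the tissue counts open to reader expectation, both for the before-after change and for its correlation with regrowth. With 15 pairs, no true change and a within-pair SD of 0.4 to 0.8 log units, the nominal 5% error would become about 8% to 16% for a 10% under-count and about 17% to 52% for a 20% under-count, and less with fewer pairs. The SDs, the size of the bias, the log scale and the paired test are assumptions, so these figures show what modest bias could do. They do not estimate bias in this trial.

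The primary SALT endpoint, the sample size, and the qPCR and serum results are untouched. This is a low-cost improvement to an exploratory analysis and does not put the trial's main conclusion in doubt.

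**What to change.** Add to Section 6.4.3, before any reading starts:
- Tissue sections receive random codes that hide subject, visit and clinical response.
- The same reader selects fields and counts in random order under code.
- The code is opened only after the counts are locked.
- Where practical, flow gating is done under the same coding after acquisition. PBMCs are stained fresh, so the staining itself cannot follow a random order.
- Optional biopsies chosen in the light of response, including those from resistant areas that Section 4.1 allows, are reported separately. Their selection precedes any reading, and coding cannot remove it.

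The cost is coded labels and a linking list kept by someone other than the reader, with no extra procedure, sample or staff. There are two drawbacks. Counts become available later, and visible follicle regrowth in a section may partly unmask the reader, so the protection is substantial but not complete.

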#### *Haplotype Analysis for CTLA4 Modulation with Abatacept Therapy*

The costimulatory pathway has demonstrated perturbations in a number of autoimmune diseases. We and others have identified haplotypes at the Costimulatory locus that confer risk for autoimmunity and alopecia areata, in particular 1,2. We hypothesize that variants carried on these haplotypes perturb the costimulatory axis and patients carrying such risk variants in particular will receive benefit from therapies specifically targeted to this pathway. Long range haplotype analysis using a small set of common SNPs across the costimulatory locus revealed two predominating haplotypes in European populations, termed 15-2-4 and 5-1-4 that are associated with autoimmune protection or risk respectively. We will analyze for the presence of haplotype susceptibility for each enrolled subject at baseline. We will utilize these results to explore whether treatment response with abatacept for AA is affected by haplotype susceptibility.

#### *Analysis of Gene Expression by Quantitative RT-PCR*

We will analyze the **transcriptional expression signature of costimulatory and IFN-response genes in the skin and PMBC of drug-treated AA patients using qPCR** as an indirect measure of the efficacy of Abatacept. Signature genes were selected based on their differential expression in affected vs. unaffected C3H mice ([name] et al. 2002), and on published studies on human AA patients vs. controls (Subramanya et al. 2010) The genes in the list represent mediators and effectors of the IFN response, which we found to be instrumental in disease pathology. Briefly, biopsies and peripheral blood from baseline and Abatacept treated patients will be collected at 0, 4, 12 and 24 week time points. RNA will be extracted from the tissues, and Sybr green-based qPCR assays will be performed. Differential gene expression resulting from inhibitor treatment will be normalized to the expression of a housekeeping gene. We expect many of the genes on this list to revert to a basal level of expression, as compared in unaffected skin of an AA patient, or skin from a healthy control.

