| 
Study Schema
 Drugs / Doses /
 Length of Treatment)
 | 
A fixed dose of abatacept (125mg) will be self-administered subcutaneously weekly for 24 weeks, with an option to extend treatment for up to an additional 24 weeks at the discretion of the investigator. A loading IV dose will not be employed.
  |

|  |  |
|--|--|
| Accrual Goal:
(Total number of subjects)              | 15   |
| Accrual Rate:
(Number of subjects expected per month) | 1-3  |
| FPFV:
LPFV:
Follow Up:
(dd-mm-yy)             | May, 1, 2013
March 31, 2015
12 months  |
| Correlative Studies:
(PK/PD, etc.)                    | 
Our published work and previous studies in human AA have reported increased NKG2DL expression and augmented expression of IFN response genes in the target hair follicle end organ, and elevated NKG2D expression in circulating CD8 T cells and NK cells (Ito et al, 2008; Petukhova et al, 2010).
 
Clinical Correlative Studies
 
Our study will include longitudinal assessment of AA biomarkers at baseline and during treatment to correlate treatment and disease status with;
 
 
1) histological improvement with reduced T cell peribulbar infiltrates.
 
2) declines in circulating and peribulbar CD8+NKG2D+ infiltration and in follicular hair follicle NKG2DL expression.
 
3) reduced IFN inflammatory biomarkers in the skin and blood.
 
4) presence or absence of AA GWAS risk haplotype
 
 |

|                                   |  |
|-----------------------------------|--|

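### The qPCR signature is normalised to a single reference gene in samples whose cell mix is expected to change, so any drift in that gene shifts every signature gene by the same factor

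*Combined protocol and SAP*

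**What the plan says.** Section 6.4.3, Analysis of Gene Expression by Quantitative RT-PCR, plans to measure costimulatory and IFN-response genes in skin and PBMC at weeks 0, 4, 12 and 24, "as an indirect measure of the efficacy of Abatacept". The material is bulk RNA: "RNA will be extracted from the tissues, and Sybr green-based qPCR assays will be performed". No sorting or microdissection step is described. Normalisation is given in one sentence: "Differential gene expression resulting from inhibitor treatment will be normalized to the expression of a housekeeping gene". The reference is singular and unnamed. The combined document gives no second reference gene, no check that the reference is stable on treatment and no adjustment for cell composition.

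The expected result is a coordinated one: "We expect many of the genes on this list to revert to a basal level of expression". The benchmark for basal level is unaffected skin of an AA patient or skin from a healthy control. The list is largely one pathway: "The genes in the list represent mediators and effectors of the IFN response".

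Elsewhere the plan expects the sampled material to change. The synopsis lists "histological improvement with reduced T cell peribulbar infiltrates" among its correlative aims. The histology plan in 6.4.3 says "We will seek evidence of resolution of total cellular infiltration (by H & E) and loss of specific" CD8+NKG2D+ cells, comparing baseline with on-treatment biopsies. The list of correlative aims in 6.4.3 also looks for declines in circulating cells, so PBMC are involved as well as skin. Under section 5.2 all subjects receive active drug.

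**The concern.** A reference gene removes differences in RNA input only if its own expression per unit of RNA stays constant between the samples compared. Here the comparison is baseline against on-treatment, and the plan predicts that infiltrate leaves the skin between the two. In bulk RNA, a gene expressed at different levels in lymphocytes, keratinocytes and follicular cells may not stay constant when their proportions change.

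Because all signature genes share one denominator, an error in it does not scatter across genes. It moves them all the same way. IFN-response genes are described in section 1.2.3 as upregulated in alopecic mouse skin, with human disease said to be alike. For genes raised in disease, a rise in reference expression would look like partial reversion, and a fall would hide a true reversion. With no concurrent untreated arm, a common shift over time has no comparison to cancel it.

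At stake is the mechanistic interpretation. Many genes moving together would be read as support for drug activity. The Biosamples text in 6.4.3 also plans to correlate resolution of inflammatory biomarkers with treatment response.

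**Working it through.** The plan states no figure on this point, so there is none to reproduce.

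**1. The common shift.** Write Δ for on-treatment minus baseline, in cycles (Ct). For gene g:

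- ΔΔCt_g = ΔCt_g − ΔCt_ref
- apparent fold change = 2^(−ΔΔCt_g), taking perfect doubling per cycle

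If gene g is truly unchanged (ΔCt_g = 0) and the reference moves by d cycles, the apparent fold change is 2^d, whichever gene it is:

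| Reference Ct shift d | −1 | −0.5 | +0.5 | +1 |
|---|---|---|---|---|
| Apparent fold change, every gene | 0.50 | 0.71 | 1.41 | 2.00 |

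A negative d means more reference transcript, so every gene looks lowered. A positive d means less, so every gene looks raised.

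**2. How often an unchanged gene would be called changed.** From the documents: 15 subjects (section 7.2). Assumed, because the documents do not give them: a two-sided paired t-test at 5% per gene, an SD of 1.0 to 1.5 cycles for the within-subject change in the normalised value, and the size of d. The test statistic is noncentral t with 14 degrees of freedom and noncentrality d√15/SD; the critical value is 2.145. For d = 0.5 and SD = 1.0, the noncentrality is 0.5 × 3.873 / 1.0 = 1.94.

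| Shift | Fold error | SD 1.0 | SD 1.5 |
|---|---|---|---|
| 0.25 cycle | 1.19 | 0.147 | 0.093 |
| 0.5 cycle | 1.41 | 0.438 | 0.225 |
| 1 cycle | 2.00 | 0.949 | 0.671 |

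The nominal rate is 0.05.

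**3. Cross-check by simulation.** With 15 subjects, 20 truly unchanged genes, SD 1.0 cycle per gene and 0.5 per reference (all but the 15 assumed), a mean shift of 0, 0.25, 0.5 or 1.0 cycle made about 5%, 13%, 36% or 89% of genes significant. About 66%, 82%, 96% or 100% of genes moved in the same direction.

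**4. Correlation with regrowth.** Let R be SALT regrowth. Then Cov(ΔΔCt_g, R) = Cov(ΔCt_g, R) − Cov(ΔCt_ref, R). If the reference moves more in subjects who regrow, the same unwanted term enters the covariance for every gene.

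**5. Effect of three references.** On the Ct scale the geometric mean is the arithmetic mean of the three Ct values. If one of the three shifts by 1 cycle, the shared error is 1/3 cycle, or 2^(1/3) = 1.26-fold. The calculation in step 2 then gives 0.225 (SD 1.0) and 0.126 (SD 1.5), against 0.949 and 0.671 with one reference. The simulation gives about 22% against 89%. If all three shift together, averaging gains nothing.

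**6. Can 15 subjects show that a reference is stable?** At the same SDs, a test on the reference's own change would miss a 0.5-cycle shift 56% (1 − 0.438) to 78% (1 − 0.225) of the time. The 95% interval half-width is 2.145 × SD/√15: 0.28 cycle at SD 0.5 and 0.55 cycle at SD 1.0. A non-significant result is therefore weak reassurance. The interval shows how large a shift remains possible.

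**The case against.** The strongest objection is that this is peripheral. The qPCR read-out is absent from section 7.3 and from both lists of secondary outcomes (2.2 and 6.4.2). No sample size or decision rule depends on it, and the plan itself calls it indirect. That stands, and it limits the weight of the point.

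A reader might infer that agreement across genes would carry no independent information. The documents and arithmetic do not support that. A shared denominator correlates the genes without erasing their own numerators: with the step 3 SDs the induced correlation is 0.25/1.25 = 0.20, and ratios between signature genes do not involve the reference at all.

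A reader might also infer that a drifting reference would reproduce exactly the predicted pattern. It would not. The plan predicts return to a basal level set by unaffected or healthy skin. A false 2-fold drop would bring a gene raised 2-fold to basal but leave one raised 8-fold at 4-fold, and would push a normal or under-expressed gene away from basal. The benchmark limits what counts as full reversion, but it does not cancel a shift over time within subjects.

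Histology and immunofluorescence, flow cytometry and serum chemokines use no reference gene and offer a partial cross-check. The plan does not say that they will be used to check the qPCR. Finally, the singular wording may be shorthand for a validated laboratory set. If so, the text should say so.

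**Conclusion.** The point holds as a modest, inexpensive improvement to an exploratory analysis. The plan specifies one unnamed reference gene, predicts changes in the cell mix of the samples, has no untreated arm, and neither guards against nor checks for drift in that gene. The 2^d effect on every gene follows from the normalisation itself.

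How much this matters depends on d, which the documents do not give. It would be wrong to infer that a shift will occur, or that false-call rates of 67 to 95% are to be expected here. Those belong to an assumed 1-cycle shift; at 0.25 cycle the range is 9 to 15%. The test and the SDs are assumptions too. Nothing here affects the SALT primary endpoint or its sample size.

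**What to change.** In section 6.4.3, replace the single reference with the geometric mean of at least three reference genes, named before the analysis. For each, report the mean change from baseline to each on-treatment time point with a 95% confidence interval, separately for skin and PBMC. Do not treat a non-significant test as proof of stability.

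Add a sentence that this reduces the shared normalisation error but does not correct for changed cell composition, which alters signature genes in bulk RNA directly. Changes in the signature should therefore be read alongside the histology, flow cytometry and serum chemokine results.

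The cost is a few sentences of text and about two more reference-gene assays per existing cDNA sample. No extra tissue, blood or visit is needed. If a validated set is already in use, only the text needs to change.
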